of pictorial & written AAPs. Our working hypothesis is that relative to usual care (Written AAP), Pictorial AAP will produce superior clinical and behavioral outcomes: (a) better treatment plan knowledge for caregiver and patient; (b) higher daily adherence rates to preventive medication (via electronic monitoring); and (c) better health outcomes (i.e., report of better asthma control & higher *lung functioning* or spirometry scores). This hypothesis is based in part on research findings indicating that use of pictures in health education markedly increases recall of information through simpler and more salient cues.

Specific Aim # 2 – Evaluate provider and family acceptability of pictorial AAP. Based on existing literature, we expect that the Pictorial AAP will be easy and user-friendly for providers to offer as well as patients and families to use. Consequently, our working hypothesis is that patient and caregiver satisfaction (e.g., perceived ease of use, benefits) survey scores will be significantly higher for the Pictorial AAP than for the Written AAP group.

Specific Aim # 3: Identify whether parent health literacy and youth literacy levels are associated with treatment outcome. Pearson (parametric) or Spearman (non-parametric) correlations will be used as appropriate to assess the association between parent health literacy and youth literacy to changes in knowledge, adherence, and health outcome, as well as caregiver and patient satisfaction, within and between AAP groups. Given that research suggests the use of graphics and images improves comprehension of medical information, it is anticipated that rural youth, particularly with lower literacy levels, will benefit significantly from a simpler, “image rich” pictorial AAP.

Design: Pilot Randomized Controlled Trial

Young people aged 8-17 were randomly assigned to one of two groups (pictorial vs. written AAP, i.e. usual care) for 6 months. The Written AAP (WAAP) group received a personalized, text-based AAP. The WAAP is consistent with national practice guidelines [5] and recommended as standard care for patients with asthma. The proposed study will use the written AAP published by the National Heart Lung and Blood Institute (NHLBI) (Available at: https://www.nhlbi.nih.gov/files/docs/public/lung/asthma_actplan.pdf). Providers (not researcher) completed the WAAP with the child's prescribed medications and specific asthma care regimen. The provider reviewed the WAAP with the child and caregiver.

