Finally, equivalence testing was conducted for all continuous outcomes, assuming that results that fall within an SD unit difference would indicate that PAAP is as good as guideline-recommended care (WAAP) with sufficient power. The overall stability of the effect of the treatment response was demonstrated utilizing the F test for equivalence of the effect of psi-squared, a standardized measure of difference between groups/time point means and an overall (across groups and time points) mean. This was be assessed utilizing output from the best-fitting general linear mixed model and by testing whether this psi-squared effect size measure falls in the critical region [6].

References

1. Akinbami, L. J., & Schoendorf, K. C. (2002). Trends in childhood asthma: Prevalence, health care utilization, and mortality. *Pediatrics*, 110(2), 315-322.
2. Akinbami, L. J., Moorman, J. E., & Liu, X. (2011). Asthma prevalence, health care use, and mortality: United States, 2005-2009 (Report No. 32). Atlanta, GA: National Health Statistics Reports, Centers for Disease Control and Prevention; <http://www.cdc.gov/nchs/data/nhsr/nhsr032.pdf>. Updated January 12, 2011. Accessed May 4, 2014.
4. Forbis, S. G., & Ailigne, C. A. (2002). Poor readability of written asthma management plans found in national guidelines. *Pediatrics*, 109, e52.
5. National Heart, Lung, and Blood Institute (2007). National Asthma Education and Prevention Program (NAEPP) Expert Panel Report 3, *Guidelines for the Diagnosis and Management of Asthma* (NIH Publication No. 08-4051).
6. Wang, F., & Amrhein, J. (2016, April 18-21). *Equivalence Tests*. Paper presented at the Proceedings of the SAS®Global Forum 2016., Las Vegas, NV

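### The equivalence margin is an SD-unit difference between PAAP and WAAP, but the test uses psi-squared around an overall mean, which does not measure that difference

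*Combined protocol and SAP*

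**What the plan says.** The closing paragraph of the Study Analysis Plan reports that "equivalence testing was conducted for all continuous outcomes". The criterion is set by "assuming that results that fall within an SD unit difference would indicate that PAAP is as good as guideline-recommended care (WAAP) with sufficient power". This is a distance between the two arms on a linear SD scale. The SD meant (baseline, pooled or residual) is not named.

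The decision is then made "utilizing the F test for equivalence of the effect of psi-squared", where psi-squared is described as "a standardized measure of difference between groups/time point means and an overall (across groups and time points) mean". The input is the best-fitting mixed model, and the last step is "testing whether this psi-squared effect size measure falls in the critical region", with a citation to a general paper on equivalence tests. The documents give no formula for psi-squared, no bound, no alpha and no rule for turning one SD between arms into a psi-squared value.

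Earlier in the Study Analysis Plan, the continuous-outcome model has Time, Group and Time by Group terms. Time is categorical in the pre-post version, which gives two arms by two times, or four cell means.

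**The concern.** An equivalence claim means only what its margin excludes. Here the margin is stated on one quantity, the arm difference, and the decision is taken on another, the spread of several means around their common mean. Two questions follow. Does some psi-squared bound correspond to one SD between arms? If so, can a reader tell that it was used?

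The conclusion that the pictorial plan matches guideline-recommended care rests on this test for every continuous outcome. If psi-squared does not track the arm difference, an outcome could pass with PAAP materially worse, or fail with the arms identical because both improved.

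**Working it through.** **Inputs.** From the documents: two arms ("randomly assigned to one of two groups (pictorial vs. written AAP, i.e. usual care) for 6 months", under Design); 45 youths recruited (Methods); a pre-post model with categorical time and Time, Group and Time by Group terms (Study Analysis Plan); a margin of one SD. Assumed, because not stated: near-equal allocation, alpha 5%, equal cell weights, and the sum form, psi² = Σ(cell mean − overall mean)² / SD². The documents give no psi-squared figure, so there is none to reproduce.

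**Step 1: does psi-squared over group-by-time cells track the arm difference?** Put both arms at 0 before treatment, WAAP at g afterwards and PAAP at g − d, in SD units. The sum of squares is g² + (g − d)², and the correction for the overall mean is (2g − d)²/4. Hence

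psi² = g² − g·d + 0.75·d².

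| Common gain g | PAAP deficit d | psi² |
|---|---|---|
| 1 | 0 (identical arms) | 1 − 0 + 0 = 1.00 |
| 1 | 0.5 | 1 − 0.5 + 0.1875 = 0.69 |
| 1 | 1 | 1 − 1 + 0.75 = 0.75 |
| 0 | 1 | 0 − 0 + 0.75 = 0.75 |

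Identical arms that both improve by 1 SD score higher than arms 1 SD apart. A bound of 0.75 puts a 1 SD deficit on the boundary but classes those identical arms as non-equivalent. A bound of 1.0 puts the identical arms on the boundary. With no gain, that bound corresponds to d = √(1/0.75) = 1.15 SD; with a gain of 1 SD, it corresponds to d = 4/3 = 1.33 SD. No single bound amounts to a one-SD arm margin. The average form divides every value by 4 and leaves the ordering unchanged, so this result does not depend on sum versus average.

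**Step 2: the simplest case, as an illustration.** With two equal arms and one post value each, each mean lies d/2 from the overall mean, so psi² = 2·(d/2)² = d²/2. One SD is psi² = 0.5, and psi = 1 is d = √2 = 1.41 SD. The equivalence F test has 1 and 43 df, and its critical value is the 5th percentile of the noncentral F with noncentrality 22.5 × the psi² bound. The observed cut-off is |d| = √(2F/22.5).

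| Bound on psi² | Critical F | Observed \|d\| must be below | P(equivalent) at d = 0 | P(equivalent) at d = 1 SD |
|---|---|---|---|---|
| 0.5 | 2.86 | 0.50 | 90% | 5% |
| 1 | 9.18 | 0.90 | over 99% | 37% |

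**Step 3: how far this depends on the layout.** Arm difference that corresponds to psi = 1:

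| Layout (no common gain) | Sum form | Average form |
|---|---|---|
| Two means | 1.41 SD | 2.00 SD |
| 2×2, deficit post only | 1.15 SD | 2.31 SD |
| 2×2, deficit at both times | 1.00 SD | 2.00 SD |
| 2×4, deficit at all three follow-ups | 0.73 SD | 2.07 SD |

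The same nominal bound can be stricter than one SD, equal to it, or looser. A 2×2 version of Step 2 (3 df, 22.5 per cell, independent errors assumed, bound psi² = 1) gives about 14 to 15% at a post-only 1 SD deficit, not 37%.

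**Step 4: is a direct test feasible?** Two one-sided tests at 5% each, margin 1 SD, arms of 22 and 23: SE = √(1/22 + 1/23) = 0.298 SD. Power at zero true difference = 2Φ(1/0.298 − 1.645) − 1 = 91% (normal approximation). With 39 children, if the six families whose last measures were at 3 months were left out, it is 86%.

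**The case against.** The strongest reply is that this is an omission, not a contradiction. The plan gives one numerical threshold, an SD unit, and names a critical region without a number; a stated margin cannot conflict with an unstated bound. The analysts may have converted it correctly, or applied the test to a group or interaction effect rather than to all cells, and the cited paper may define psi-squared. That stands, and it is why the documents cannot be said to contain two incompatible thresholds.

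A reader might go further and infer that PAAP would be declared as good as WAAP at true deficits up to 1.4 SD. The documents do not support this. The figure needs psi = 1 as the bound, the sum form and two means, none of which is stated. Even then, 1.41 SD is the edge of the null region, where equivalence is declared only 5% of the time. Nor is a result that is both significantly worse and equivalent an error in itself, since any test with a non-zero margin can produce it. It would signal a fault only if the wrong bound had been used.

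The reply does not remove the main point. As the plan words it, psi-squared is measured from a mean over arms and time points together, and Step 1 shows that such a quantity cannot be converted to an arm difference by any choice of bound. Reporting the bound alone would not cure that.

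**Conclusion.** The concern holds in a limited form. The stated margin and the tested quantity are on different scales. No formula, bound, alpha or conversion is given, and psi-squared over group-by-time cells does not isolate PAAP versus WAAP. In the 2×2 layout, identical arms with a 1 SD common gain score 1.0, against 0.75 for a 1 SD deficit without gain and 0.69 for a 0.5 SD deficit with that gain. This rests on reading the definition as group-by-time cell means with equal weights, which is the natural reading. If only two arm means were used, a conversion exists and the defect reduces to an unreported bound.

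The size of any error in the reported conclusions cannot be determined. The 37% against 5% is one labelled scenario. Where the deficit is present at every follow-up, psi = 1 maps to about 0.7 to 2.3 SD in the layouts tried, so the bound used could have been too strict as well as too loose. The documents do not show that any particular equivalence conclusion is wrong. They do leave a reader unable to say what deficit was excluded.

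**What to change.** Base the equivalence conclusion on the arm contrast itself. For each continuous outcome, take the model-based PAAP minus WAAP difference at the final time point, or in change from baseline, and apply two one-sided tests at 5% (90% CI) against the stated one-SD margin. Name the SD that defines the margin. Report as equivalent only those outcomes whose interval lies wholly inside it.

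If the psi-squared test is kept as a secondary analysis, state its formula, the means it covers, the alpha, the bound, and how the bound follows from the margin. A conversion of margin²/2 is valid only for two equal arms and the sum form; with the average form the one-SD value would be 0.25, not 0.5.

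The cost is a short amendment to the analysis text and a small re-analysis of existing model output, with no new data. Some equivalence claims may become less favourable. Power at zero true difference stays at about 90% with 45 children (Step 4).

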This pilot RCT began data collection in May 2017 and continued through May 2018. A total of 45 youths and their families were recruited. Data was collected at four time points: baseline (recruitment), 1-month, 3-months, and 6-months. At baseline, caregivers completed a general information form on demographics and medical history, as well as measures to assess health status (Asthma Control Test), and health literacy (S-TOFHLA and Asthma Numeracy Questionnaire). Patients completed measures to assess health status (Asthma Control Test), health literacy (S-TOFHLA) and reading comprehension (WIAT-III), and complete pulmonary function testing (spirometry). Qualitative methods were used to gather acceptability and feasibility data. Participants in both groups were provided with their first canister or diskus of medication in order to attach the electronic adherence monitor at baseline. Participants refilled with medications they purchase as needed for the remainder of the study. One month after initial visit, families were called to complete the Asthma Control Test and study-specific satisfaction survey. Three months after initial visit, families returned to clinic for follow up with the physician and to complete the Asthma Control Test, AAP knowledge interview, and pulmonary function testing (patient only). Six months after initial visit, families returned to clinic for follow up with the physician and to complete the Asthma Control Test, AAP knowledge interview, satisfaction survey, spirometry (patient only), and to review adherence data and return the inhaler monitor. Six families completed follow up measures at 3 months due to time constraints.

The findings of this study will be relevant to research and practice with rural youths with asthma, as well as families with significant literacy issues. A novel and innovative stakeholder-led approach was used in this study to develop a more accessible and effective approach to asthma education in pediatric settings. The process and findings of this study will be widely disseminated and guide improvements to the PAAP for use in future research and practice, including the possible development of an "app" version of the PAAP.

Study Analysis Plan

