All analysis was conducted using SAS 9.4. Descriptive analysis was conducted on baseline measures for both the total sample, and by treatment group. Frequency and valid percentages were used to describe categorical data, means and standard deviations for continuous data, and medians and interquartile range for non-normal continuous data. Group differences were tested by chi-square, Fisher's exact, Mann-Whitney, or t-test as appropriate for variable type, with odds ratios (OR) and 95% CI of the OR, means by group and t-statistic, or mean score ranks and Z-statistic reported.

Generalized linear mixed model (GLIMMIX) with multinomial response distribution and a cumulative logit link function were used to analyze the daily adherence data, in order to model the ordinal outcome measure (0%, 25%, 50%, 75%, and 100% adherence) over time. Multiple covariance structure models were tested, with an unstructured matrix best fitting by AIC. Because adherence changed depending on prescription, the models were tested by both interaction of prescription and by stratification. Sensitivity analysis was also run for 3 months or less data and compared to the full 6 month dataset. Fixed effects were reported. Generalized linear mixed model (GLIMMIX) with binary response distribution was also conducted for the binary outcome of ACT cut-off ≥ 19 .

Linear mixed models with restricted estimation maximum likelihood estimation and Kenward-Richardson adjustment for the degrees of freedom were used for the continuous outcome data. Pre-post analysis included combining 3 month and 6 month time points for outcome measures where the final time point was 3 instead of 6 months. Time was treated as categorical for these pre- post- time points; otherwise time was treated as continuous variable. Time, Group, and Time by Group interaction effects were included in the model. Random effects statement included the time, with participants listed by ID. Different covariance structures and intercept inclusion were tests; AIC was used to determine best model fit with the best fitting model including no intercept and an unstructured covariance matrix. Fixed effects are reported. Sensitivity analysis was also run by including days in the study for those post-outcomes where some participants have 3 months or less data and compared to the full 6 month dataset.

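### The equivalence test as described mixes change shared by both arms with the gap between arms, so it does not test whether the pictorial plan is within one SD of the written plan; its bound is also not given

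*Combined protocol and SAP*

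**What the plan says.** The last paragraph of the Study Analysis Plan covers all continuous outcomes. Its aim is between arms: "assuming that results that fall within an SD unit difference would indicate that PAAP is as good as guideline-recommended care (WAAP) with sufficient power". It then describes one procedure, "utilizing the F test for equivalence of the effect of psi-squared", and defines the quantity as "psi-squared, a standardized measure of difference between groups/time point means and an overall (across groups and time points) mean". The decision is made by "testing whether this psi-squared effect size measure falls in the critical region", with a citation to a conference paper on equivalence tests.

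The means come from the linear mixed models of the preceding paragraph, where "Time, Group, and Time by Group interaction effects were included in the model". For the pre-post analyses, "Time was treated as categorical for these pre- post- time points", so those outcomes have four cells: two arms by two times.

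The margin is given in words only. The plan does not say which SD is meant (baseline, residual or change), what alpha is used, how one SD between arms converts to psi-squared, or whether psi-squared is summed or averaged over cells. It describes no PAAP-minus-WAAP equivalence contrast, confidence interval or pair of one-sided tests.

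**The concern.** The question is whether two arms differ by less than one SD. The statistic asks instead whether all arm-by-time means lie close to one common mean. If both arms improve by the same amount, the means spread out over time and the statistic rises, although the arms do not differ at all. Shared improvement is plausible here: under Design and Methods, both arms receive a personalised plan reviewed by the provider, and a first canister or diskus of medication.

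This is the only analysis in the plan that can support a claim that PAAP is as good as guideline-recommended care. Depending on the unstated bound, it could withhold that claim from identical arms that both improve, or grant it to a PAAP that is a full SD worse. A reader of the plan cannot tell which. The superiority comparisons (Group, Time by Group) are not affected.

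**Working it through.** The documents give no psi-squared bound, alpha or power figure for this test, so there is no stated figure to reproduce.

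**Inputs from the documents.** 45 youths recruited (Methods); model terms Time, Group and Time by Group; a pre-post layout with categorical time; margin of 1 SD.

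**Assumptions.** Arms of 22 (WAAP) and 23 (PAAP); equal true baselines; unit SD; baseline-to-post correlation 0.5 (range 0.3 to 0.7); alpha 0.05.

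**1. What psi-squared measures.** Summed over the four cells, psi-squared = sum of (cell mean - overall mean)^2 / SD^2. In a balanced 2x2 layout this equals G^2 + T^2 + D^2/4, where G is the average gap between arms, T the average change over time and D the difference in change. With equal baselines and a follow-up gap d, G = d/2 and D = d, so psi-squared = d^2/2 + T^2.

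| WAAP change / PAAP change (SD) | Follow-up gap d | T | Psi-squared |
|---|---|---|---|
| +0.5 / +0.5 | 0 | 0.5 | 0.25 |
| +0.8 / +0.8 | 0 | 0.8 | 0.64 |
| +1.0 / +1.0 | 0 | 1.0 | 1.00 |
| +0.5 / -0.5 | 1 | 0 | 0.50 |
| +1.0 / 0 | 1 | 0.5 | 0.75 |
| +1.2 / +0.2 | 1 | 0.7 | 0.99 |
| +1.5 / +0.5 | 1 | 1.0 | 1.50 |

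A 1 SD gap has no single psi-squared value. Identical arms score worse than arms at +0.5/-0.5 once the shared change exceeds sqrt(0.50) = 0.71 SD, and worse than arms of which only one moves by 1 SD once it exceeds sqrt(0.75) = 0.87 SD. Averaging instead of summing divides every value by 4 and keeps the order.

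**2. A check that needs no equivalence bound.** The Wald statistic for equality of the four cell means, allowing for the within-person correlation r, is t^2 x 45 / (2(1 - r)) for a shared change t. At t = 0.8 and r = 0.5 that is 0.64 x 45 / 1 = 28.8, against 15.0 for +0.5/-0.5. At r = 0.3 it is 20.6 against 12.4; at r = 0.7, 48.0 against 22.1. The inversion remains.

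**3. Chance of declaring equivalence.** This uses 20,000 simulated trials per scenario. Equivalence is declared if estimated psi-squared is below (3/22.5) x the 5% point of a noncentral F with 3 and 86 df and noncentrality 22.5 x bound. The cut-offs are 0.192, 0.486 and 2.64 for summed bounds 0.5, 1 and 4; a summed bound of 4 is an averaged bound of 1. This reference distribution treats the cells as independent; it is an assumption, not plan text.

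| Truth | Summed bound 0.5 | Summed bound 1 | Averaged bound 1 |
|---|---|---|---|
| Identical, no change | 84% | 98% | over 99% |
| Identical, +0.3 | 55% | 95% | over 99% |
| Identical, +0.5 | 18% | 76% | over 99% |
| Identical, +0.8 | 0.3% | 16% | over 99% |
| Identical, +1.0 | under 0.3% | 1.5% | over 99% |
| PAAP 1 SD worse, +0.5/-0.5 | 5% | 40% | over 99% |
| PAAP 1 SD worse, one arm unchanged | under 5% | 13% | over 99% |
| PAAP 1 SD worse, +1.2/+0.2 | under 5% | 3% | over 99% |
| PAAP 1 SD worse, +1.5/+0.5 | under 5% | 0.1% | 95% |

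Over correlations 0.3 to 0.7 at summed bound 1, identical arms at +0.8 pass 13% to 19% and +0.5/-0.5 passes 38% to 42%.

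**4. Direct test of the stated claim.** Two one-sided tests of the follow-up difference at a 1 SD margin: SE = sqrt(1/22 + 1/23) = 0.298 and t(43) at 0.95 = 1.681, so the 90% CI half-width is about 0.501. Identical arms pass if the observed gap is within about 0.499, or 1.67 SE, which has probability about 0.90. Using the difference in change also gives 90%, and baseline adjustment 97%, at correlation 0.5. Over 0.3 to 0.7 the ranges are 75% to 99% and 92% to 99.7%. A PAAP 1 SD worse passes 5%. Shared change does not enter.

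**5. Other layouts.** With four visits and a sustained effect (eight cells, as for the Asthma Control Test), a shared change t gives 1.5t^2. Identical arms at +1 SD then score 1.50, the same as arms +0.5/-0.5 apart at all three follow-ups; at +0.8 SD they score 0.96. For AAP knowledge (listed at 3 and 6 months) and satisfaction (1 and 6 months) Methods lists no baseline. There a constant gap d scores d^2 and a shared change t between visits scores t^2, so the two still cannot be told apart.

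**The case against.** The strongest reply is about reading. The paragraph has two steps, and the psi-squared test is introduced as showing the stability of the treatment response. It may mean one psi-squared per model effect; for the Time by Group term, shared change cancels and the inversion disappears. That reading is possible. But the definition names a mean across both groups and time points, and the plan does not say which effect would carry the verdict. If it were the Group main effect, a 1 SD gap present only at follow-up would be averaged with a zero baseline gap and counted as 0.5 SD. If the psi-squared test is a separate analysis, the 1 SD claim has no described test.

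Second, a summed bound of 0.5 or less would be a valid, conservative test, because any 1 SD gap forces psi-squared to at least 0.5. With no shared change it passes identical arms 84% of the time. This stands: under such a bound the fault is lost power, not false equivalence. But the plan does not state that bound, and with a bound of 1, gaps up to sqrt(2) = 1.41 SD lie inside the equivalence region.

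Third, the inversion at 0.8 SD belongs to the two-time layout; with four visits there is only a tie, at 1 SD. False passes at bound 1 also fade when both arms improve. Both points stand, but the mixing of shared change with the gap remains in every layout.

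Fourth, the cited paper may contain the critical region, and every pass rate rests on assumed inputs. The rates are illustrations, not this trial's error rates. The algebra in step 1 needs only a balanced 2x2 layout.

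Finally, this is a pilot with superiority hypotheses, and data collection ended in May 2018. That limits the weight of the point and means any re-analysis is post hoc.

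**Conclusion.** The concern holds. As written, the test does not match the conclusion drawn from it: psi-squared over all arm and time-point means responds to shared change as well as to the gap between arms, and the 1 SD margin is never converted to its scale. In the pre-post layout, identical arms improving 0.8 SD score 0.64 against 0.50 for arms a full SD apart.

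Of the bounds examined, none both passes identical arms reliably when they improve together and holds a PAAP 1 SD worse to about 5%. A summed bound of 0.5 controls false equivalence but passes identical arms only 18% of the time at +0.5 SD. A summed bound of 1 passes a PAAP 1 SD worse up to 40% of the time, and an averaged bound of 1 at least 95%. These rates depend on the assumed arm sizes, correlation, alpha and F reference; the mismatch does not. A failure cannot be read as a difference between arms, and a pass cannot be interpreted until the bound is known.

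**What to change.** Base the equivalence conclusion on two one-sided tests, reported as a 90% CI, of the single PAAP-minus-WAAP contrast at follow-up, obtained with an ESTIMATE or LSMESTIMATE statement from the existing mixed model and compared with the plan's 1 SD margin. State the reference SD and alpha. Use a baseline-adjusted contrast where a baseline was collected (Asthma Control Test, spirometry) and an unadjusted one where none is listed (AAP knowledge, satisfaction). For knowledge, first confirm that there was no baseline, because Specific Aim # 3 refers to changes in knowledge. Report change over time separately.

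If psi-squared is kept, restrict it to the group contrast and state its bound and scaling. Either way, label the re-analysis post hoc and show it beside the original result.

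The cost is a few lines of SAS and a paragraph of text, with no new data. Equivalence verdicts for some outcomes may change.

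### The psi-squared equivalence test pools repeated measures on the same children without saying how within-child correlation enters its critical region, so the limit tested is not shown to be 1 SD

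*Combined protocol and SAP*

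**What the plan says.** The closing paragraph of the Study Analysis Plan applies equivalence testing to every continuous outcome, "assuming that results that fall within an SD unit difference would indicate that PAAP is as good as guideline-recommended care (WAAP) with sufficient power". The test is an F test on psi-squared, described as "a standardized measure of difference between groups/time point means and an overall (across groups and time points) mean". It is to be "assessed utilizing output from the best-fitting general linear mixed model", and the decision is made "by testing whether this psi-squared effect size measure falls in the critical region". A conference paper on equivalence tests (reference 6) is cited. No formula, alpha, degrees of freedom or psi-squared limit is printed.

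The preceding paragraph describes the mixed model: "Random effects statement included the time, with participants listed by ID", with an unstructured covariance chosen by AIC. Methods gives the sample, "A total of 45 youths and their families were recruited", and the visits: baseline, 1, 3 and 6 months. The AAP knowledge interview is listed at 3 and 6 months and the satisfaction survey at 1 and 6 months, so both visits follow delivery of the plan. Spirometry and the Asthma Control Test also have a baseline value.

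**The concern.** The aim concerns one quantity, the difference between arms in SD units. The statistic covers all group-by-visit cells at once. The usual critical region for an F test on psi-squared comes from a noncentral F whose noncentrality is the cell size times the limit, which holds when cell means are independent with a common SD. Here the visit means within an arm come from the same children and are correlated.

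If the F is computed with that correlation in the model, its noncentrality at a 1-SD arm difference is no longer the assumed value. If it is computed without, the statistic does not follow the reference distribution. Either way the error rate at 1 SD moves with rho, which differs by outcome and is not reported. The statement that the pictorial plan is as good as guideline care rests on this test, and Methods says the findings will be widely disseminated and guide further development.

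**Working it through.** The plan gives no equivalence figure to reproduce, so this is a check of how the test behaves.

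**Inputs from the documents.** 45 children; two groups ("randomly assigned to one of two groups (pictorial vs. written AAP, i.e. usual care) for 6 months"); target of 1 SD; psi-squared over group and time-point means; repeated visits per child.

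**Assumptions, because the documents are silent.** Split 22/23 (mean 22.5 per arm); two visits; equal SD; alpha 5%; psi-squared limit 1; rho 0.5 to 0.8; the usual independent-cell noncentral-F region.

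**Step 1: the limit.** In a 2 x 2 layout, an arm difference of d SD at both visits puts each cell d/2 from the grand mean, so psi-squared = 4 x (d/2)^2 = d^2. A limit of 1 therefore matches d = 1 for this pattern.

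**Step 2: the critical value.** The 5% quantile of the noncentral F with 3 and 86 df and noncentrality 22.5 x 1 = 22.5 is 3.647. Equivalence is declared when F is at or below it.

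**Step 3: the effect of rho on the mixed-model F.** The visit-averaged arm contrast has variance (1 + rho) times its independent-cell value. Its noncentrality is therefore 22.5 d^2/(1 + rho), and setting this equal to 22.5 gives an effective limit of d = sqrt(1 + rho) SD:

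- rho 0.5: noncentrality at d = 1 is 22.5/1.5 = 15; effective limit 1.22 SD.
- rho 0.8: 22.5/1.8 = 12.5; effective limit 1.34 SD.

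**Step 4: rate of declaring equivalence at a true 1-SD difference at both visits** (100,000 simulated trials per setting):

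| Version of the statistic | rho 0 | rho 0.5 | rho 0.8 |
|---|---|---|---|
| Cell-mean F, pooled SD | 5.1% | 10.3% | 13.5% |
| Mixed-model F, unstructured covariance | 5.0% | 19.6% | 29.0% |
| Cell-mean F, within-child residual SD | 5.5% | 1.9% | 0.6% |

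At rho 0 all three are near 5%, so the departures come from the correlation. With 43 denominator df the mixed-model row becomes 18.5% and 27.6% at rho 0.5 and 0.8. With 39 children, should the six families who finished at 3 months drop out of the comparison, the three rows run 10.4-14.1%, 17.9-26.1% and 2.3-0.9%.

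**Step 5: pre-post outcomes.** A difference of d at the post visit only gives psi-squared = 3(d/4)^2 + (3d/4)^2 = 0.75 d^2. With d set so that psi-squared equals 1 (d = 1/sqrt(0.75) = 1.15 SD), the rates at rho 0, 0.5 and 0.8 are 4.7%, 3.4% and 1.8% (pooled SD) and 4.5%, 0.3% and about 0% (mixed-model F). Against its own limit the test is conservative here. At exactly d = 1, psi-squared is 0.75, inside the limit. The pooled-SD rates are then 14.1%, 12.7% and 10.8%, and the mixed-model rates 13.6%, 2.1% and about 0%. One limit on psi-squared is thus not one limit on the arm difference.

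**Step 6: four visits.** With the limit kept at 1 and a 1-SD difference at all visits, rho 0.5 to 0.8 gives 2.0-5.0% (pooled SD) and 9.7-21.0% (mixed-model F).

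**The case against.** The strongest reply is that the documents do not print the critical region. They cite a paper for it and say that the test uses output from a model that does carry the within-child covariance. That the region assumes independent cells is an inference from the usual form of the named test. This stands, and it is why the rates above are conditional.

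A reader might infer that false equivalence is shown to be inflated two- to six-fold. The documents do not support that. With a within-child residual SD the rate is below 5%. It is also below 5% if the Group F alone is used with a two-group 1-SD limit: the noncentrality at the limit is 22.5 x 0.5 = 11.25, the true value is 22.5/(1 + rho), and the rate is 1.6% at rho 0.5 and 3.4% at rho 0.8. A reader might also run the first two rows of the table together as one 10-29% range due to rho, but these are two different statistics, about 10-14% and 19-29%.

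The inflated scenario is narrow as well. It fits outcomes with two post-baseline visits. Where one visit is baseline, randomization makes a true 1-SD difference at both visits implausible.

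Modelling the covariance does not settle the matter, however. Step 3 shows that an F which respects the correlation still moves the limit to sqrt(1 + rho) SD unless the critical region is adjusted too, and no adjustment is described.

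**Conclusion.** The concern holds in conditional form. The plan states a 1-SD aim for the arm difference but tests a pooled group-by-time quantity on correlated means, and leaves the limit, alpha, SD, F statistic and handling of correlation unstated. Under the usual region, error at a 1-SD difference is about 5% only when rho is 0. For rho 0.5 to 0.8 and two post-baseline visits it runs from about 0.5% to 29%, depending on which statistic was used. For pre-post outcomes with a post-only difference, the test tends to be conservative against its own limit.

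These figures rest on the 22/23 split, two visits, psi-squared limit 1, alpha 5% and the assumed rho range, none of which the documents give. Control of false equivalence at 1 SD is therefore not demonstrated. Neither is its failure in a particular direction.

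**What to change.** Replace the psi-squared region with two one-sided tests (equivalently a 90% CI) on the PAAP-minus-WAAP contrast from the fitted mixed model. Use that contrast's own standard error and adjusted df, and limits of plus or minus 1 between-child SD in outcome units. State alpha and the source of the SD.

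The choice of contrast matters:

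- **Pre-post outcomes:** use the post-visit or change-from-baseline contrast. Averaging in baseline halves a post-only difference; in simulation a post-only 1-SD difference was then declared equivalent in 54-75% of trials.
- **Outcomes with only post-baseline visits:** use the visit-averaged or final-visit contrast.

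In simulation the contrast-based test held 4.7-5.2% error at the 1-SD limit at every rho tried. Power with equal arms was 93-97% for the two-visit average (rho 0.5 to 0.8). For a single visit, SE = sqrt(1/22 + 1/23) = 0.298 SD, and power is about 2 x Phi(1/0.298 - 1.68) - 1 = 90%. A change contrast multiplies that SE by sqrt(2(1 - rho)), so it loses power when rho is below 0.5.

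If psi-squared is kept, name the F and the SD. Obtain the 5% critical value for each outcome by simulating from the fitted covariance with the arms exactly at the limit.

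The cost is a few lines of SAS, a revised paragraph and no new data. The downside is somewhat lower power for single-visit contrasts, and some outcomes may no longer meet equivalence.
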